#### 4.2.5.6 Supplementary Analyses of the Secondary Endpoint #3

Not Applicable.

#### 4.2.5.7 Subgroup Analyses

Subgroup analyses will be performed using separate negative binomial regression models, as per section 4.2.5.4, by presence of heart failure (Yes/No, identified per Medical History using an SMQ of “Cardiac Failure”; SMQ Code: 20000004), RAASi use at screening (Yes/No, identified per Concomitant Medication eCRF as CMCLASCD in (‘C09AA’, ‘C09BA’, ‘C09BB’, ‘C09BX’, ‘C09CA’, ‘C09DA’, ‘C09DB’, ‘C09DX’, ‘C09XA’) where Start Date is prior to date of informed consent), CKD stage, without diagnosis of CKD (but eGFR  $<90$  ml/min/1.73m^2), baseline  $K^+$  ( $5.0 < K^+ \leq 5.5$  versus  $5.5 < K^+ \leq 6.5$  mmol/L) at baseline and an alternative baseline  $K^+$  categorisation ( $5.0 < K^+ \leq 5.5$ ,  $5.5 < K^+ \leq 6.0$ , and  $6.0 < K^+ \leq 6.5$  mmol/L) at baseline. Subgroup analyses will only be conducted providing there are 10 or more events per subgroup category.

### 4.2.6 Secondary Endpoint #4 (RAASi down-titration)

*Time to first occurrence of RAASi down-titration (or discontinuation) at any time post-discharge up to 180 days*

#### 4.2.6.1 Definition

- Population: Full analysis set
- Endpoint: Time to first occurrence of RAASi down-titration (or discontinuation) at any time post-discharge up to 180 days.
- Intercurrent event strategy: Participants who discontinue of treatment will continue to be followed up to the first component of the composite endpoint (treatment policy strategy). Participants who die of any cause or are lost to follow-up will be censored at their date of death or loss to follow-up respectively. Participants who do not have an

event by 180 days post-discharge will be administratively censored at the date of 180 days post-discharge.

- Population level summary (analysis): Kaplan-Meier plots of the survival function for the SZC and SoC treatment groups will be presented. Log-rank test for testing will be used to calculate a two-sided p-value, Cox proportional hazards ratio for estimation, with randomised treatment group (reference level SoC) as the independent variable. The HR and the two-sided 95% confidence interval will be presented. The risk difference and two-sided 95% confidence interval will be presented (as per section 4.2.3.2) at 180 days post-discharge.

#### **4.2.6.2 Derivations**

Time to first occurrence will be defined as the earliest date of (date of RAASI down-titration (or discontinuation), all-cause death, date of loss to follow-up, date of 180 days post-discharge) – date of randomization + 1.

#### **4.2.6.3 Handling of Dropouts and Missing Data**

Participants who are lost to follow-up will be censored at the date of discontinuation as recorded on the participant's disposition form.

#### **4.2.6.4 Primary Analysis of Secondary Endpoint #4**

The primary analysis of this secondary endpoint will be performed as per section 4.2.3.4.

#### **4.2.6.5 Sensitivity Analyses of the Secondary Endpoint #4**

Sensitivity analyses of this secondary endpoint will be performed as per section 4.2.3.5 excluding the sensitivity analysis for RAASI down-titration.

#### **4.2.6.6 Supplementary Analyses of the Secondary Endpoint #4**

Not Applicable.

#### **4.2.6.7 Subgroup Analyses**

Subgroup analyses will be performed using separate Cox models, as per section 4.2.3.4, by presence of heart failure (Yes/No, identified per Medical History using an SMQ of "Cardiac Failure"; SMQ Code: 20000004), RAASI use at screening (Yes/No, identified per Concomitant Medication eCRF as CMCLASCD in ('C09AA', 'C09BA', 'C09BB', 'C09BX', 'C09CA', 'C09DA', 'C09DB', 'C09DX', 'C09XA') where Start Date is prior to date of informed consent), CKD stage, without diagnosis of CKD (but eGFR <90 ml/min/1.73m^2), baseline K+ (5.0 < K+ ≤ 5.5 versus 5.5 < K+ ≤ 6.5 mmol/L) at baseline and an alternative baseline K+ categorisation (5.0 < K+ ≤ 5.5, 5.5 < K+ ≤ 6.0, and 6.0 < K+ ≤ 6.5 mmol/L) at baseline. Subgroup analyses will only be conducted providing there are 10 or more events per subgroup category.

#### **4.2.7 Secondary Endpoint #5 (Hospital admission or ED visit with HK)**

*Time to first occurrence of any component of all-cause hospital admission or ED visit with HK as a contributing factor at any time post-discharge up to 180 days.*

##### **4.2.7.1 Definition**

- Population: Full analysis set
- Endpoint: Time to first occurrence of either component of the composite outcome at any time post-discharge up to 180 days.
- Intercurrent event strategy: Participants who discontinue treatment or who have hospital admission or ED visit without HK as a contributing factor will continue to be followed up to the first component of the composite endpoint (treatment policy strategy). Participants who die of any cause, use rescue therapy for HK or are lost to follow-up will be censored at the date of death, use of rescue therapy or loss to follow-up respectively. Participants who have RAASI down-titration (including discontinuation) will continue to be followed up to the first component of the composite endpoint (treatment policy strategy). Participants who do not have an event by 180 days post-discharge will be administratively censored at the date of 180 days post-discharge.
- Population level summary (analysis): Kaplan-Meier plots of the survival function for the SZC and SoC treatment groups will be presented. Log-rank test for testing will be used to calculate a two-sided p-value, Cox proportional hazards ratio for estimation, with randomised treatment group (reference level SoC) as the independent variable. The HR and the two-sided 95% confidence interval will be presented. The risk difference and two-sided 95% confidence interval will be presented (as per section 4.2.3.2) at 180 days post-discharge.

##### **4.2.7.2 Derivations**

Time to first occurrence will be defined as the earliest date of (all-cause hospital admission or ED visit with HK as a contributing factor, all-cause death, use of rescue therapy for HK, date of loss to follow-up, date of 180 days post-discharge) – date of randomization + 1.

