- Population level summary (analysis): Kaplan-Meier plots of the survival function for the SZC and SoC treatment groups will be presented. Log-rank test for testing will be used to calculate a two-sided p-value, Cox proportional hazards ratio for estimation, with randomised treatment group as the independent variable. The HR and the two-sided 95% confidence interval will be presented. The risk difference and two-sided 95% confidence interval will be presented.
- Sensitivity analyses will be conducted as per secondary endpoint #1 excluding the sensitivity analysis for RAASI down-titration.

3. Number of all-cause hospital admission, or ED visits with HK as a contributing factor, at any time post-discharge up to 180 days.

- Population: FAS
- Endpoint: Number of all-cause hospital admissions or ED visits with HK as a contributing factor at any time post-discharge up to 180 days.
- Intercurrent event strategy: Participants who discontinue treatment, use rescue therapy for HK or who have an ED visit without HK as a contributing factor, will continue to be followed up to the first component of the composite endpoint (treatment policy strategy). Participants who die of any cause or are lost to follow-up will be censored at the date of death or loss to follow-up. Participants who have RAASI down-titration (including discontinuation) will continue to be followed up to the first component of the composite endpoint (treatment policy strategy).
- Population level summary (analysis): Mean number of all-cause hospital admissions or ED visits with HK as a contributing factor by randomised treatment group. Negative binomial regression model with randomised treatment group as the independent variable

and including duration of time in study as an offset. The incidence rate (SZC/SoC), along with 95% confidence intervals and two-sided p-values will be displayed.

- Sensitivity analyses will be conducted using the PPS analysis population and a multivariable negative binomial regression model including age (as a spline), sex, presence of heart failure, diabetes, RAASi use, CKD stage and baseline K⁺ (mild HK defined by K⁺ between > 5.0 and ≤ 5.5 mmol/L and moderate/severe HK defined by K⁺ between > 5.5 and ≤ 6.5 mmol/L) as independent variables.

4. Time to first occurrence of any component of hospital admission or ED visit, both with HK as a contributing factor at any time post-discharge up to 180 days.

- Population: FAS

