**Table 5: Testing order for primary and secondary efficacy endpoints**

Order	Efficacy Endpoint	Section
1	Occurrence (yes/no) of normokalaemia (NK) ( $K^+$ between 3.5 and 5.0 mmol/L, inclusive) at 180 days post-discharge	4.2.2
2	Time to first occurrence of all-cause hospital admission or ED visit with HK as a contributing factor, or all-cause death, or use of rescue therapy for HK at any time post-discharge up to 180 days inclusive.	4.2.3
3	Time to first occurrence of all-cause hospital admission or ED visit with HK as a contributing factor at any time post-discharge up to 180 days inclusive.	4.2.4
4	Number of all-cause hospital admission or ED visits with HK as a contributing factor, at any time post-discharge up to 180 days.	4.2.5
5	Time to first occurrence of RAASI down-titration (or discontinuation) at any time post-discharge up to 180 days.	4.2.6
6	Time to first occurrence of hospital admission or ED visit, both with HK as a contributing factor at any time post-discharge up to 180 days.	4.2.7
7	Number of hospital admission or ED visits, both with HK as a contributing factor, at any time post-discharge up to 180 days.	4.2.8

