Secondary	Time to first occurrence of hospital admission or ED visit, both with HK as a contributing factor at any time post-discharge up to 180 days.	FAS	Participants who discontinue treatment or who have hospital admission or ED visit without HK as a contributing factor will continue to be followed up to the first component of the composite endpoint (treatment policy strategy). Participants who die of any cause, use rescue therapy for HK or are lost to follow-up will be censored at the date of death, use of rescue therapy or loss to follow-up respectively.	Kaplan-Meier plots of the survival function for the SZC and SoC treatment groups will be presented. Log-rank test for testing will be used to calculate a two-sided p-value. Cox proportional hazards ratio for estimation with randomised treatment group as the independent variable. The HR and the two-sided 95% confidence interval will be presented. The risk difference and two-sided 95% confidence interval will be presented.	4.2.7
Objective 7: evaluate the effect of continuing SZC as part of the discharge medications, compared to SoC, in reducing the number of hospital admissions or ED visits with HK as a contributing factor					
Secondary	Number of hospital admission or ED visits with HK as a contributing factor, at any	FAS	Participants who discontinue treatment, use rescue therapy for HK or who have a hospital admission, or an ED visit without HK as a contributing factor, will	Mean number of hospital admissions or ED visits, with HK as a contributing factor by randomised	4.2.8

Statistical category	Endpoint	Population	Intercurrent event strategy	Population level summary (analysis)	Details in section
	time post-discharge up to 180 days.		continue to be followed up to the first component of the composite endpoint (treatment policy strategy). Participants who die of any cause or are lost to follow-up will be censored at the date of death or loss to follow-up. Participants who have RAASi down-titration (including discontinuation) will continue to be followed up to the first component of the composite endpoint (treatment policy strategy).	treatment group. Negative binomial regression model with randomised treatment group as the independent variable and including duration of time in study as an offset. The incidence rate (SZC/SoC), along with 95% confidence intervals and two-sided p-values will be displayed.	

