#### **4.2.4.2 Derivations**

Time to first occurrence will be defined as the earliest date of (all-cause hospital admission, ED visits with HK as a contributing factor, all-cause death, use of rescue therapy for HK, date of loss to follow-up, date of 180 days post-discharge) – date of randomization + 1.

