##### **4.2.7.4 Primary Analysis of Secondary Endpoint #5**

The primary analysis of this secondary endpoint will be performed as per section 4.2.3.4.

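### The SAP derives secondary endpoint #5 from all-cause admissions although the endpoint is defined as hyperkalaemia-related, so step 6 of the testing hierarchy would repeat step 3

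*SAP*

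**What the plan says.** The endpoint is secondary #5 in the SAP and #4 in the protocol.

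These places require HK for both the admission and the ED visit:

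- SAP 3.3.4, Table 5, order 6: "Time to first occurrence of hospital admission or ED visit, both with HK as a contributing factor".
- SAP 4.2.1, Objective 6: "Time to first occurrence of hospital admission or ED visit, both with HK as a contributing factor at any time".
- Protocol 9.4.3.2, secondary endpoint 4: "Time to first occurrence of any component of hospital admission or ED visit, both with HK as a contributing factor at any time". Protocol Table 3 agrees.
- SAP 4.2.7.1, intercurrent events: a participant with a "hospital admission or ED visit without HK as a contributing factor will continue to be followed up", so a non-HK admission is not an event. The heading of 4.2.7 also omits all-cause.

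These places count any admission:

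- SAP 4.2.7, endpoint line: "Time to first occurrence of any component of all-cause hospital admission or ED visit with HK as a contributing factor".
- SAP 4.2.7.2, derivation: "Time to first occurrence will be defined as the earliest date of (all-cause hospital admission or ED visit with HK as a contributing factor", followed by death, rescue therapy, loss to follow-up and Day 180.

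SAP section 2 lists only the Per Protocol Set and ECG changes as departures from the protocol, so this is not a declared change.

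**The concern.** A derivation section is what a programmer works from. Here it contradicts the intercurrent-event rule directly above it, and it describes a different endpoint that already sits at step 3 of the hierarchy. If it is followed, a formally tested hypothesis is replaced by a copy of one already tested. The result would carry the Table 5 label, so an all-cause finding could be reported as HK-specific. Step 7 (HK-related counts) would also open without a genuine HK-specific test in front of it.

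A smaller mismatch of the same kind appears in SAP 4.2.5.5. The mean-cumulative-count sensitivity analysis uses HK-related admissions only as its recurring event. That is not secondary #3 (all-cause admissions plus HK ED visits), nor secondary #6 (HK admissions plus HK ED visits), which inherits it through 4.2.8.5. It lies outside the hierarchy and is run only if loss to follow-up differs by more than 10% between arms.

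**Working it through.** **1. Secondary #2 and #5 side by side**

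| Item | Secondary #2 (step 3), SAP 4.2.4 | Secondary #5 (step 6), SAP 4.2.7 |
|---|---|---|
| Population | FAS | FAS |
| Endpoint line | all-cause admission or HK ED visit | same words |
| Derivation: events | "Time to first occurrence will be defined as the earliest date of (all-cause hospital admission, ED visits with HK as a contributing factor" | all-cause admission or HK ED visit |
| Derivation: other dates | death, rescue, loss to follow-up, Day 180 | same |
| Time origin | date of randomisation, + 1 | same |
| Censoring | death, rescue, loss to follow-up, Day 180 | same |
| Primary analysis | section 4.2.3.4 | "The primary analysis of this secondary endpoint will be performed as per section 4.2.3.4" |
| Non-event encounters | non-HK ED visit only | non-HK ED visit **and** non-HK admission |

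Only the last row differs, and the 4.2.7.2 derivation contradicts it. With every other row equal, the log-rank statistic and hazard ratio are identical. Under SAP 3.3.4 each step is tested only if the preceding null is rejected, so step 6 is reached only after step 3 has rejected. As derived, step 6 then rejects with probability 1.

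**2. The plan's own figure**

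Protocol 9.2.2 gives the only time-to-event sizing: 17% vs 43.2% with an event, HR 0.329, 5% significance, 80% power.

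- HR = ln(0.83)/ln(0.568) = 0.329.
- Freedman events, two-sided: (1.96 + 0.842)² × (1.329/0.671)² = 30.8, so 31.
- Mean event proportion (0.17 + 0.432)/2 = 0.301; 31/0.301 = 103, so 52 per arm (N = 104).
- Dropout: 104/0.8 = 130; 130/0.8 = 162.5, so 163.

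The stated size reproduces and is not in dispute.

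**3. How far the two readings differ**

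The HK share of admissions, f, is not in the documents. It is assumed here at 10% to 50%, equal in both arms. The other inputs are the 9.2.2 rates: admission 40% SoC and 16.2% SZC; HK ED visit 3.2% and 0.8%.

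Adding components as the protocol does:

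- p_SoC = 0.40f + 0.032; p_SZC = 0.162f + 0.008
- HR = ln(1 − p_SZC)/ln(1 − p_SoC)
- d = 52(p_SoC + p_SZC)
- power = Φ(√d (1 − HR)/(1 + HR) − 1.96)

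| f | p_SoC | p_SZC | HR | Events d | Power |
|---|---|---|---|---|---|
| 0.10 | 7.2% | 2.4% | 0.328 | 5.0 | 0.20 |
| 0.25 | 13.2% | 4.9% | 0.351 | 9.4 | 0.31 |
| 0.50 | 23.2% | 8.9% | 0.353 | 16.7 | 0.50 |
| 1 (all-cause reading) | 43.2% | 17.0% | 0.329 | 31.3 | 0.81 |

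Non-HK admissions would make up (31.3 − 16.7)/31.3 = 47% to (31.3 − 5.0)/31.3 = 84% of the events counted under 4.2.7.2.

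**4. Simulation of step 6 given step 3**

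Settings: 4,000 trials per scenario, 52 per arm, independent exponential times, no dropout, rescue or death. Here f multiplies the admission hazard rather than the admission proportion, so event counts and power come out a little above the table.

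| f | Events, intended step 6 | Power, intended step 6 | P(intended step 6 rejects, given step 3 rejects) | Same, as derived |
|---|---|---|---|---|
| 0.10 | 5.6 | 0.21 | 0.24 | 1 |
| 0.25 | 10.4 | 0.37 | 0.43 | 1 |
| 0.50 | 17.8 | 0.60 | 0.69 | 1 |

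A further scenario gives SZC no effect on HK-related events and lets the whole all-cause difference come from non-HK admissions. The derived test then rejects in about 75% (f = 0.10) and 73% (f = 0.25) of trials. The intended test rejects in about 5%.

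**The case against.** **The intent is clear.** The heading, the intercurrent-event rule, Table 5, the overview and the protocol all point the same way, and the endpoint line of 4.2.7 matches that of 4.2.4 word for word. It looks like carried-over text, and a careful programmer following 4.2.7.1 would build the right endpoint. That stands as an explanation. It does not make the two subsections compatible: the time in 4.2.7.2 ends at the first admission of any cause, whereas 4.2.7.1 requires follow-up to continue past a non-HK admission.

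**The derivation sets a time, not an event flag.** It lists event and censoring dates together, so duplication is conditional on all-cause admissions being flagged as events. This is right. But taking the 4.2.7.2 time with an HK-only flag would censor participants at non-HK admissions, which 4.2.7.1 also rules out.

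**The wording could be read as HK applying to both components.** It groups admission and ED visit in one item. The reading is weak, because the SAP uses similar wording for endpoints that really are all-cause.

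**The figures are soft.** The HK share is assumed, and the closed-form and simulated results come from slightly different models, so the power in one table should not be combined with the conditional probabilities in the other. Low power at step 6 also belongs to the intended endpoint, not to the wording error. All of this is accepted. The figures only illustrate how different the two tests are; the contradiction does not depend on them.

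**The reach is narrow.** Step 6 matters only if steps 1 to 5 all reject, including RAASi down-titration, for which no power is given. That stands, and so does the point that the mean-cumulative-count text is a side issue. The protocol plans that method only for exploratory endpoint #6.

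**Conclusion.** The concern holds. SAP 4.2.7 and 4.2.7.2 define a formally tested endpoint in a way that conflicts with 4.2.7.1, Table 5, the SAP overview and the protocol. If it is programmed as derived, step 6 reproduces step 3 exactly and the HK-specific time-to-first-event hypothesis is not tested. Reading the passages side by side is enough to establish this.

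The practical size depends on the unknown HK share of admissions. For assumed shares of 10% to 50%, the intended test would also reject in roughly a quarter to two thirds of trials where step 3 rejects; the derived test always would.

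The limits are clear. The primary endpoint, the main secondary endpoint and N = 104 are unaffected. Family-wise error over distinct hypotheses is not inflated, because a repeated test adds no new hypothesis. HK-related counts are still tested at step 7. The harm is a mislabelled result and an empty gate before step 7. This must be corrected because it sits in the specification of a hierarchically tested endpoint.

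**What to change.** - **SAP 4.2.7 (endpoint line) and 4.2.7.2:** replace the all-cause wording with hospital admission or ED visit, both with HK as a contributing factor as adjudicated. State that non-HK admissions are neither events nor censoring, in line with 4.2.7.1.
- **SAP 4.2.5.5 (lesser point):** set the recurring event to match the endpoint analysed, that is, all-cause admissions plus HK ED visits for #3, and HK admissions plus HK ED visits for #6. Removing the analysis for these two endpoints would also resolve the mismatch, since the protocol does not ask for it there.

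The cost is text edits in three places. No new data are needed: SAP 4.2 already provides for blinded adjudication of HK contribution. The documents do not say whether code exists; if it was written from 4.2.7.2, the event flag and the time variable need changing and the analysis rerunning. The edit should be made before database lock so that the choice cannot appear to follow the results.

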##### **4.2.7.3 Handling of Dropouts and Missing Data**

Participants who are lost to follow-up will be censored at the date of discontinuation as recorded on the participant's disposition form.

##### **4.2.7.4 Primary Analysis of Secondary Endpoint #5**

The primary analysis of this secondary endpoint will be performed as per section 4.2.3.4.

##### **4.2.7.5 Sensitivity Analyses of the Secondary Endpoint #5**

Sensitivity analyses of this secondary endpoint will be performed as per section 4.2.3.5.

#### **4.2.7.6 Supplementary Analyses of the Secondary Endpoint #5**

Not Applicable.

#### **4.2.7.7 Subgroup Analyses**

Subgroup analyses will be performed using separate Cox models, as per section 4.2.3.4, by presence of heart failure (Yes/No, identified per Medical History using an SMQ of “Cardiac Failure”; SMQ Code: 20000004), RAASI use at screening (Yes/No, identified per Concomitant Medication eCRF as CMCLASCD in (‘C09AA’, ‘C09BA’, ‘C09BB’, ‘C09BX’, ‘C09CA’, ‘C09DA’, ‘C09DB’, ‘C09DX’, ‘C09XA’) where Start Date is prior to date of informed consent), CKD stage, without diagnosis of CKD (but eGFR <90 ml/min/1.73m^2), baseline K+ (5.0 < K+ ≤ 5.5 versus 5.5 < K+ ≤ 6.5 mmol/L) and an alternative baseline K+ categorisation (5.0 < K+ ≤ 5.5, 5.5 < K+ ≤ 6.0, and 6.0 < K+ ≤ 6.5 mmol/L) at baseline. Subgroup analyses will only be conducted providing there are 10 or more events per subgroup category.

#### **4.2.8 Secondary Endpoint #6 (Number of hospital admissions or ED visits with HK)**

*Number of hospital admissions or ED visits with HK as a contributing factor, at any time post-discharge up to 180 days.*

